2.2.4 Tolerability endpoints

The tolerability endpoints are based on vaginal bleeding pattern and include the following variables:

Bleeding:

- Number of subjects with bleeding by treatment day, treatment cycle and reference period (summary of cycles 2-4, 5-7, 8-10, 11-13 and 2-13)
- Number of subjects with unscheduled bleeding days by treatment cycle and reference period
- Number of subjects with scheduled bleeding days by treatment cycle and reference period
- Number of subjects with prolonged bleeding >nine days/ >14 days by reference period
- Number of bleeding episodes during treatment and by reference period
- Number of days with bleeding by cycle and reference period
- Number of days with unscheduled bleeding by cycle and reference period
- Number of days with scheduled bleeding by cycle and reference period
- Mean length of bleeding episodes by cycle and reference period

Spotting:

- Number of subjects with spotting by treatment day, treatment cycle and reference period (summary of cycles 2-4, 5-7, 8-10, 11-13 and 2-13)
- Number of subjects with unscheduled spotting days by treatment cycle and reference period
- Number of subjects with scheduled spotting days by treatment cycle and reference period
- Number of subjects with prolonged spotting >nine days/ >14 days by reference period
- Number of spotting episodes during treatment and by reference period
- Number of days with spotting by cycle and reference period
- Number of days with unscheduled spotting by cycle and reference period
- Number of days with scheduled spotting by cycle and reference period
- Mean length of spotting episodes by cycle and reference period

Only cycles of women with complete and correct diary entries will be taken into account in the analysis.

All tolerability variables will be evaluated over 13 cycles.

Another tolerability endpoint is the IMP acceptability.

Tolerability Endpoints in Addition to the Protocol

In addition, tolerability endpoints that are based on vaginal bleeding pattern and on combined variables (bleeding/spotting) will be evaluated:

- Number of subjects with bleeding/spotting by treatment day, treatment cycle and reference period
- Number of subjects with unscheduled bleeding/spotting days by treatment cycle and reference period
- Number of subjects with scheduled bleeding/spotting days by treatment cycle and reference period
- Number of subjects with no bleeding/spotting days by treatment cycle and reference period

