2.6 Sample Size

At least 920 subjects will be allocated to treatment to have at least 5000 evaluable cycles for the PI calculation in non-breastfeeding women aged ≤ 35 years (at the time of trial enrollment). Additionally, a minimum of 75 subjects aged > 35 years will be allocated to treatment. The calculations are based on empirical values including firstly a rate of 24.8% of subjects using back-up contraception or not having intercourse. Secondly, 45% of subjects are assumed to drop out of the trial. The prime target is to collect at least 5000 evaluable cycles.

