5.7.1 Bleeding Pattern

The number and rate of subjects with different bleeding and spotting patterns will be presented for each cycle. The Clopper-Pearson 95% CI for vaginal bleeding or spotting rate of subjects will be calculated using the **PROC FREQ** procedure:

```
PROC FREQ DATA=<data set>;
  BY <by variable>;
  TABLES <endpoint variable> / BINOMIAL;
RUN;
```

The following definitions will be applied:

Episode of bleeding/spotting – bleeding/spotting days bounded on either end by two days of no bleeding or spotting. Missing data will be considered as bleeding/spotting day if it is bounded on bleeding/spotting days or one days of no bleeding or spotting.

Days of bleeding/spotting – presence of bleeding/spotting on actual day.

Scheduled bleeding/spotting – any bleeding or spotting that occurs during hormone-free intervals (defined as Days 25-28 ± 1 day). Bleeding/spotting that starts during this period and continues for up to eight consecutive days is considered as scheduled bleeding/spotting.

If scheduled bleeding starts in Cycle X but ends in Cycle (X+1) then bleeding episode will be assigned to Cycle X.

Any bleeding or spotting that occurs during cycle Days [1-8] of the first treatment cycle and lasts up to 8 consecutive bleeding/spotting days will also be considered as scheduled bleeding days.

Unscheduled bleeding/spotting – any bleeding/spotting that occurs outside the time window defined for scheduled bleedings.

Cumulative rate of subjects with different bleeding and spotting patterns for reference periods (summary of cycles 2-4, 5-7, 8-10 and 11-13) will be provided. Cumulative rates only for reference periods will also be presented for number and percent of subjects with prolonged bleeding and spotting > 9 days/ > 14 days and the number of bleeding and spotting episodes.

Number and percent of days per cycle and reference period with bleeding and spotting, scheduled bleeding, unscheduled bleeding, scheduled spotting or unscheduled spotting and duration of scheduled bleeding, scheduled spotting, unscheduled bleeding and unscheduled spotting will be analyzed descriptively.

Cycles without consecutively missing diary entries and with less than five non-consecutive missing diary entries will be used in the bleeding pattern analysis.

Tables

No.	Name	Analysis set	Comments

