Table 15.4.1.1.1	Number of Subjects with Bleeding by Treatment Day, Treatment Cycle and Reference Period	Full Analysis	Number and percentage of subjects in respective time point will be presented. Percentage will be based on the number of subjects with respective cycles available. Data of centers 104 and 120 will be excluded.
Table 15.4.1.2.1	Number of Subjects with Unscheduled Bleeding Days by Treatment Cycle and Reference Period	Full Analysis	Number and percentage of subjects in respective time point will be presented. Percentage will be based on the number of subjects with respective cycles available. Data of centers 104 and 120 will be excluded.
Table 15.4.1.3.1	Number of Subjects with Scheduled Bleeding Days by Treatment Cycle and Reference Period	Full Analysis	Number and percentage of subjects in respective time point will be presented. Percentage will be based on the number of subjects with respective cycles available. Data of centers 104 and 120 will be excluded.
Table 15.4.1.4.1	Number of Days with Bleeding by Cycle and Reference Period	Full Analysis	Number of days will be summarized as continuous data. Number of days will be based on the number of subjects with respective cycles available. Data of centers 104 and 120 will be excluded.
Table 15.4.1.5.1	Number of Days with Unscheduled Bleeding by Cycle and Reference Period	Full Analysis	Number of days will be summarized as continuous data. Number of days will be based on the number of subjects with respective cycles available. Data of centers 104 and 120 will be excluded.
Table 15.4.1.6.1	Number of Days with Scheduled Bleeding by Cycle and Reference Period	Full Analysis	Number of days will be summarized as continuous data. Number of days will be based on the number of subjects with respective cycles available. Data of centers 104 and 120 will be excluded.
Table 15.4.2.1.1	Number of Subjects with Spotting by Treatment Day, Treatment Cycle and Reference Period	Full Analysis	Number and percentage of subjects in respective time point will be presented. Percentage is based on subject with respective cycle available. Data of centers 104 and 120 will be excluded.
Table 15.4.2.2.1	Number of Subjects with Unscheduled Spotting Days by Treatment Cycle and Reference Period	Full Analysis	Number and percentage of subjects in respective time point will be presented. Percentage will be based on the number of subjects with respective cycles available. Data of centers 104 and 120 will be excluded.

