Table 15.4.4.1.1 _add	Number of Subjects with Bleeding/Spotting by Treatment Day, Treatment Cycle and Reference Period	Full Analysis	Number and percentage of subjects in respective time point will be presented. Percentage will be based on the number of subjects with respective cycles available. Data of centers 104 and 120 will be excluded.
Table 15.4.4.2.1 _add	Number of Subjects with Unscheduled Bleeding/Spotting Days by Treatment Cycle and Reference Period	Full Analysis	Number and percentage of subjects in respective time point will be presented. Percentage will be based on the number of subjects with respective cycles available. Data of centers 104 and 120 will be excluded.
Table 15.4.4.3.1 _add	Number of Subjects with Scheduled Bleeding/Spotting Days by Treatment Cycle and Reference Period	Full Analysis	Number and percentage of subjects in respective time point will be presented. Percentage will be based on the number of subjects with respective cycles available. Data of centers 104 and 120 will be excluded.
Table 15.4.5.1.1 _add	Number of Subjects with no Bleeding/Spotting Days by Treatment Cycle and Reference Period	Full Analysis	Number and percentage of subjects in respective time point will be presented. Percentage will be based on the number of subjects with respective cycles available. Data of centers 104 and 120 will be excluded.
Table 15.4.6.1.1 _add	Number of Days with Bleeding/Spotting by Cycle and Reference Period in BMI Groups	Full Analysis	Number of days will be summarized as continuous data. Number of days will be based on the number of subjects with respective cycles available. Data of centers 104 and 120 will be excluded.
Table 15.4.6.2.1 _add	Number of Days with Unscheduled Bleeding/Spotting by Cycle and Reference Period in BMI Groups	Full Analysis	Number of days will be summarized as continuous data. Number of days will be based on the number of subjects with respective cycles available. Data of centers 104 and 120 will be excluded.
Table 15.4.6.3.1 _add	Number of Days with Scheduled Bleeding/Spotting by Cycle and Reference Period in BMI Groups	Full Analysis	Number of days will be summarized as continuous data. Number of days will be based on the number of subjects with respective cycles available. Data of centers 104 and 120 will be excluded.

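### Bleeding results over several cycles have no entry rule and no scaling in the tables, which matters for cycles 2-13 and only modestly for the 3-cycle periods

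*SAP*

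**What the plan says.** SAP section 5.7.1 gives most bleeding and spotting tables both by cycle and by longer period. For the tables that count women, the usual note is "Percentage will be based on the number of subjects with respective cycles available". For the tables that count days, it is "Number of days will be based on the number of subjects with respective cycles available", and the days are summarised as a continuous variable.

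The longer periods come from section 2.2.4, which gives "reference period (summary of cycles 2-4, 5-7, 8-10, 11-13 and 2-13" in its first bleeding item and its first spotting item. Section 4.6 lists 2-13 separately, as an overall period. The text of 5.7.1 and the protocol synopsis name only the four 3-cycle periods.

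Diary validity is defined for single cycles only: "Cycles without consecutively missing diary entries and with less than five non-consecutive missing diary entries will be used in the bleeding pattern analysis".

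One scaled measure is promised. The text of 5.7.1, like the protocol synopsis under statistical methods, plans "Number and percent of days per cycle and reference period with bleeding and spotting". Its denominator is not given, and no table specification or appendix table title in the SAP carries a percentage of days.

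On follow-up, SAP section 2.6 states that "45% of subjects are assumed to drop out of the trial".

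**The concern.** For a single cycle the note on available cycles is clear. For 3 or 12 cycles it can mean that a woman enters with any valid cycle, or only with all of them. The two rules produce different tables from the same data.

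Under the any-cycle rule, a woman seen for two cycles adds a two-cycle total to a 12-cycle mean. If neither cycle had bleeding, she also counts as bleed-free for the whole period. Day totals, episode counts and the share of women with any bleeding are then pulled down, and the share with none is pushed up. Under the all-cycles rule, totals cover the full period, but 2-13 describes only women who stayed to the end and lost no cycle to the diary rule.

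Demonstrating tolerability is a secondary objective (SAP section 2.1.2), and the bleeding pattern is most of its content. A 12-cycle summary is likely to be quoted, and a reader could not tell which rule produced it.

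**Working it through.** **The plan's own figure.** The 45% dropout is used in the sample size, together with "a rate of 24.8% of subjects using back-up contraception or not having intercourse". The SAP shows no formula. If dropouts contribute no cycles, each subject yields 13 × (1 − 0.45) × (1 − 0.248) = 5.377 evaluable cycles. Then 5000 / 5.377 = 930 subjects, and 920 subjects give 4947 cycles. Both are close to the stated 920 and 5000. That convention is conservative for sizing but says nothing about when women leave, so the timing below is assumed.

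**Inputs.** Retention S(k) is the share of women with cycle k, and S(13) = 0.55. Three assumed shapes:
- even: S(k) = 1 − 0.45k/13
- constant hazard: S(k) = 0.55^(k/13)
- front-loaded: 60% of the dropout by cycle 4, the rest evenly afterwards

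No diary loss is assumed at first. The 45% and the 920 belong to the sizing for non-breastfeeding women aged 35 or under. They are applied here to the Full Analysis Set as an approximation.

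**Any-cycle rule, day totals.** Mean cycles observed = (sum of S(k) over the period) / S(first cycle). Shortfall = 1 − mean / period length, taking bleeding days per cycle as constant. For 2-13 with even dropout, the sum is 12 − 0.45 × 90/13 = 8.885 and S(2) = 0.931. The mean is 8.885 / 0.931 = 9.55 cycles and the shortfall is 1 − 9.55/12 = 20.5%.

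| Shape | Women entering 2-13 (of 920) | Mean cycles of 12 | Shortfall 2-13 | Shortfall 2-4 | Shortfall 11-13 |
|---|---|---|---|---|---|
| Even | 856 | 9.55 | 20.5% | 3.7% | 5.6% |
| Constant hazard | 839 | 9.44 | 21.4% | 4.4% | 4.4% |
| Front-loaded | 796 | 9.32 | 22.3% | 7.8% | 3.4% |

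Over all four 3-cycle periods and all three shapes, the shortfall runs from 2.8% to 7.8%.

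**Any-cycle rule, no bleeding.** Assume each woman has her own chance of a bleed-free cycle, distributed Beta(0.6, 1.4) with mean 30%. The chance of no bleeding in j cycles is P(j) = B(0.6 + j, 1.4) / B(0.6, 1.4), where B is the beta function, so P(12) = 1.9%. With even dropout, j = 1 to 11 each have weight (0.45/13) / 0.931 = 0.037, and j = 12 has weight 0.55 / 0.931 = 0.591. The weighted mean of P(j) is 4.4%, or 2.3 times the full-period value.

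The factor depends heavily on the assumption. With a mean chance of 20-40% and within-woman correlation of 0.3-0.6, over the three shapes, it is 1.2 to 5.6 for 2-13 and 1.03 to 1.29 for 2-4.

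**All-cycles rule.** Dropout alone leaves 0.55 × 920 = 506 women (55%) for 2-13. If each cycle independently passes the diary rule with probability q, the share is 0.55 × q^12:
- q = 0.98: 43% (397 women)
- q = 0.95: 30% (273 women)
- q = 0.90: 16% (143 women)

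The documents give no value for q. If lost cycles cluster in the same women, the reduction is smaller.

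**The case against.** The best reply is that the plan does scale: percent of days per reference period is a time-adjusted measure, promised in both documents. So a reader who infers that nothing is normalised goes too far. But the measure has no denominator (nominal or observed days), reaches no table, and cannot help the yes/no rows or the episode counts.

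Second, SAP section 4.1 defers percentage denominators to table footnotes, and section 3.3 lets the data review meeting settle open SAP issues. A rule may therefore appear later. However, that meeting follows database lock in an open-label, single-arm trial, so the choice could be made with the results in view. A footnote also would not scale a day count.

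Third, it is not certain that every table will have a 2-13 row. The item on women without bleeding in 2.2.4 says only reference period, and 4.6 keeps 2-13 apart. The row is probable. This uncertainty stands, and it is part of what needs clarifying.

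Fourth, these are descriptive tables, and the per-cycle rows have no partial-period problem. That also stands, and it limits the weight of the point.

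**Conclusion.** The point holds, chiefly for cycles 2-13. With 45% dropout and no diary loss, an any-cycle rule leaves 2-13 day totals about 21% short (20-22% over the three shapes) and overstates absence of bleeding, by an amount that depends on the assumed variation between women. An all-cycles rule limits 2-13 to at most about 55% of women. For 3-cycle periods the effect on day totals is modest: about 4-6% under even or constant-hazard dropout, and 3-8% over all shapes.

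A reader might infer three stronger conclusions that the documents do not support:
- **Tolerability looks better under either rule.** This is not shown for the all-cycles rule. It would require women who leave to bleed more, which is plausible but not stated.
- **Only a small group remains for 2-13.** Dropout alone leaves 55%. Smaller shares need a diary loss that the documents do not quantify.
- **The 3-cycle periods are badly distorted.** This too would need substantial diary loss.

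The Pearl Index is not involved. The change should be made, because neither rule gives a satisfactory 2-13 result and the remedy is cheap.

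**What to change.** In SAP section 5.7.1 and the table specifications, for every period longer than one cycle:

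1. Report days as 28 × bleeding days / valid diary days. This is equivalent to the percent of valid days and so delivers the measure already promised. State whether missing days that the episode definition counts as bleeding enter the numerator and the divisor.
2. State the minimum number of valid cycles for a woman to enter each 3-cycle period and 2-13, and show the number of women and valid cycles contributing.
3. For 2-13, give the percentage of valid cycles with no bleeding, with bleeding and with unscheduled bleeding alongside any yes/no row.
4. Say which tables carry a 2-13 row, so that sections 2.2.4, 4.6 and 5.7.1 agree.

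The cost is SAP wording and a divisor in the programming, with no new data. Some period figures may become less favourable. Scaling does not remove selection if women leave because of bleeding, so trends across periods still need to be read with the contributing numbers beside them.

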5.7.2 IMP Acceptability

IMP acceptability will be summarized by default frequency tabulation. Shift tables will be provided to illustrate change from V3 to V6/EDV. Additionally, for subjects who switched from another oral contraceptive to the study medication default frequency tables will be summarized to present change of subject wellbeing.

Tables

No.	Name	Analysis set	Comments
Table 15.4.7.1.1	IMP Acceptability Assessment	Full Analysis	Number and percentage will be presented. Percentage will be based on the number of subjects with non-missing data.
Table 15.4.7.2.1	Shift table for IMP Acceptability Assessment	Full Analysis	Number and percentage showing changes between Visit 3 and Visit 6/EDV will be presented. Percentage will be based on FAS.

Listings

No.	Name	Analysis set	Comments
Listing 16.2.10.1	IMP Acceptability Assessment	Full Analysis	IMP acceptability assessment records will be listed.

6. INTERIM ANALYSIS

No interim analysis is planned.

8. APPENDICES

- 1. Specification of Tables**
- 2. Specification of Listings**
- 3. Specification of Figures**
- 4. Tables**

Appendix tables defined below will be provided in separate .rtf files for each output.

Seq. No	Table No and Title	Output file name
Baseline Characteristics		
1.	Table 15.1.1.1.1 Analysis Sets – Enrolled Set	T15_01_01_01_01_anal_sets_es
2.	Table 15.1.2.1.1 Screen Failures – Enrolled Set	T15_01_02_01_01_scr_fail_es
3.	Table 15.1.3.1.1 Reasons for Exclusion from Analysis Sets – Enrolled Set	T15_01_03_01_01_excl_anal_es
4.	Table 15.1.4.1.1 Subjects' Disposition – Safety Set	T15_01_04_01_01_dispos_ss
5.	Table 15.1.4.1.2 Subjects' Disposition (Excluding Site 140) – Safety Set	T15_01_04_01_02_dispos_wo140_ss
6.	Table 15.1.5.1.1 Disposition by Attended Visit – Safety Set	T15_01_05_01_01_dispos_visit_ss
7.	Table 15.1.6.1.1 Disposition by Sites – Safety Set	T15_01_06_01_01_dispos_sites_ss
8.	Table 15.1.7.1.1 Deviations Leading to Pregnancies Exclusion from the Method Failure Analysis – Modified Full Analysis Set	T15_01_07_01_01_dev_met_fail_mfas
9.	Table 15.1.7.1.2 Deviations Leading to Cycles Exclusion from Analyses – Modified Full Analysis	T15_01_07_01_02_dev_cyc_mfas
10.	Table 15.1.8.1.1 Demographics – Safety Set	T15_01_08_01_01_demo_ss
11.	Table 15.1.8.1.2 Demographics – Modified Full Analysis Set	T15_01_08_01_02_demo_mfas
12.	Table 15.1.9.1.1 Subgroups – Safety Set	T15_01_09_01_01_subgr_ss
13.	Table 15.1.9.1.2 Subgroups – Modified Full Analysis Set	T15_01_09_01_02_subgr_mfas
14.	Table 15.1.10.1.1 Baseline Characteristics at Screening – Safety Set	T15_01_10_01_01_base_char_ss
15.	Table 15.1.10.1.2 Baseline Characteristics at Screening – Modified Full Analysis Set	T15_01_10_01_02_base_char_mfas
16.	Table 15.1.11.1.1 Substance Use – Safety Set	T15_01_11_01_01_substance_ss
17.	Table 15.1.12.1.1 Prior Medical History Conditions – Safety Set	T15_01_12_01_01_prior_mh_ss
18.	Table 15.1.12.2.1 Current Medical History Conditions – Safety Set	T15_01_12_02_01_current_mh_ss
19.	Table 15.1.13.1.1 Gynecological History – Safety Set	T15_01_13_01_01_gin_his_ss
20.	Table 15.1.14.1.1 VTE Risk Factors – Safety Set	T15_01_14_01_01_vte_ss
21.	Table 15.1.15.1.1 Menstrual History – Safety Set	T15_01_15_01_01_menstr_his_ss
22.	Table 15.1.16.1.1 Prior Medications, Therapies and Contraception – Safety Set	T15_01_16_01_01_prior_cm_ss
23.	Table 15.1.16.2.1 Concomitant Medications, Therapies and Contraception – Safety Set	T15_01_16_02_01_concom_cm_ss
24.	Table 15.1.17.1.1 Exposure to Investigational Medicinal Product – Safety Set	T15_01_17_01_01_exp_ss
25.	Table 15.1.18.1.1 Number of Subjects with at Least One Missing Entry of IMP Intake in Treatment Diary by Treatment Cycle and Overall – Safety Set	T15_01_18_01_01_mis_imp_ss
26.	Table 15.1.19.1.1 Number of Subjects with Gaps between Two Active Tablet Intakes of More Than 48 Hours by Treatment Cycle and Overall – Safety Set	T15_01_19_01_01_48h_gap_intake_ss
27.	Table 15.1.20.1.1 Compliance to Investigational Medicinal Product – Safety Set	T15_01_20_01_01_compl_ss
Efficacy Data		
28.	Pearl Index Based on Evaluable Cycles in Non-Breastfeeding Women Aged ≤ 35 Years (Only Confirmed Pregnancies, Excluding Sites 104 and 120) – Modified Full Analysis Set	T15_02_01_01_01_PI_eval_less_35_C_E_mfas

29.	Table 15.2.1.2.1	Overall Pearl Index in Non-Breastfeeding Women (Only Confirmed Pregnancies, Excluding Sites 104 and 120) – Modified Full Analysis Set	T15_02_01_02_01_PI_over_C_E_mfas
30.	Table 15.2.1.2.2	Overall Pearl Index in Non-Breastfeeding Women Aged \leq 35 Years (Only Confirmed Pregnancies, Excluding Sites 104 and 120) – Modified Full Analysis Set	T15_02_01_02_02_PI_over_less_35_C_E_mfas
31.	Table 15.2.1.2.3	Overall Pearl Index in Non-Breastfeeding Women Aged $>$ 35 Years (Only Confirmed Pregnancies, Excluding Sites 104 and 120) – Modified Full Analysis Set	T15_02_01_02_03_PI_over_more_35_C_E_mfas
32.	Table 15.2.1.2.4_add	Overall Pearl Index in Non-Breastfeeding Women by BMI Subgroup (Only Confirmed Pregnancies, Excluding Sites 104 and 120) – Modified Full Analysis Set	T15_02_01_02_04_PI_over_BMI_C_E_mfas
33.	Table 15.2.1.2.5_add	Overall Pearl Index in Non-Breastfeeding Women by BMI Subgroup (Only Confirmed Pregnancies, Including Sites 104 and 120) – Modified Full Analysis Set	T15_02_01_02_05_PI_over_BMI_C_I_mfas
34.	Table 15.2.1.2.6_add	Overall Pearl Index in Non-Breastfeeding Women by BMI Subgroup (Confirmed and Suspected, Non-confirmed Pregnancies, Excluding Sites 104 and 120) – Modified Full Analysis Set	T15_02_01_02_06_PI_over_BMI_CS_E_mfas
35.	Table 15.2.1.2.7_add	Overall Pearl Index in Non-Breastfeeding Women by BMI Subgroup (Confirmed and Suspected, Non-confirmed Pregnancies, Including Sites 104 and 120) – Modified Full Analysis Set	T15_02_01_02_07_PI_over_BMI_CS_I_mfas
36.	Table 15.2.1.2.8_add	Overall Pearl Index in Non-Breastfeeding Women by Weight Subgroup (Only Confirmed Pregnancies, Excluding Sites 104 and 120) – Modified Full Analysis Set	T15_02_01_02_08_PI_over_weight_C_E_mfas
37.	Table 15.2.1.2.9_add	Overall Pearl Index in Non-Breastfeeding Women by Weight Subgroup (Only Confirmed Pregnancies, Including Sites 104 and 120) – Modified Full Analysis Set	T15_02_01_02_09_PI_over_weight_C_I_mfas
38.	Table 15.2.1.2.10_add	Overall Pearl Index in Non-Breastfeeding Women by Weight Subgroup (Confirmed and Suspected, Non-confirmed Pregnancies, Excluding Sites 104 and 120) – Modified Full Analysis Set	T15_02_01_02_10_PI_over_weight_C_S_E_mfas
39.	Table 15.2.1.2.11_add	Overall Pearl Index in Non-Breastfeeding Women by Weight Subgroup (Confirmed and Suspected, Non-confirmed Pregnancies, Including Sites 104 and 120) – Modified Full Analysis Set	T15_02_01_02_11_PI_over_weight_C_S_I_mfas
40.	Table 15.2.1.3.1	Pearl Index for Method Failures in Non-Breastfeeding Women (Only Confirmed Pregnancies, Excluding Sites 104 and 120) – Modified Full Analysis Set	T15_02_01_03_01_PI_mf_C_E_mfas
41.	Table 15.2.1.3.2	Pearl Index for Method Failures in Non-Breastfeeding Women Aged \leq 35 Years (Only Confirmed Pregnancies, Excluding Sites 104 and 120) – Modified Full Analysis Set	T15_02_01_03_02_PI_mf_less_35_C_E_mfas
42.	Table 15.2.1.3.3	Pearl Index for Method Failures in Non-Breastfeeding Women Aged $>$ 35 Years (Only Confirmed Pregnancies, Excluding Sites 104 and 120) – Modified Full Analysis Set	T15_02_01_03_03_PI_mf_more_35_C_E_mfas
43.	Table 15.2.1.4.1	Pearl Index Based on Evaluable Cycles in Non-Breastfeeding Women (Only Confirmed Pregnancies, Excluding Sites 104 and 120) – Modified Full Analysis Set	T15_02_01_04_01_PI_eval_C_E_mfas
44.	Table 15.2.1.4.2	Pearl Index Based on Evaluable Cycles in Non-Breastfeeding Women Aged $>$ 35 Years (Only Confirmed Pregnancies, Excluding Sites 104 and 120) – Modified Full Analysis Set	T15_02_01_04_02_PI_eval_more_C_E_mfas
45.	Table 15.2.1.4.3_add	Pearl Index Based on Evaluable Cycles in Non-Breastfeeding Women Aged \leq 35 Years	T15_02_01_04_03_PI_eval_less_35_C_I_mfas

	(Only Confirmed Pregnancies, Including Sites 104 and 120) – Modified Full Analysis Set	
46.	Table 15.2.1.4.4_add Pearl Index Based on Evaluable Cycles in Non-Breastfeeding Women Aged \leq 35 Years (Confirmed and Suspected, Non-confirmed Pregnancies, Excluding Sites 104 and 120) – Modified Full Analysis Set	T15_02_01_04_04_PI_eval_less_35_C_S_E_mfas
47.	Table 15.2.1.4.5_add Pearl Index Based on Evaluable Cycles in Non-Breastfeeding Women Aged \leq 35 Years (Confirmed and Suspected, Non-confirmed Pregnancies, Including Sites 104 and 120) – Modified Full Analysis Set	T15_02_01_04_05_PI_eval_less_35_C_S_I_mfas
48.	Table 15.2.1.4.6_add Pearl Index Based on Evaluable Cycles in Non-Breastfeeding Women Aged \leq 35 Years by BMI Subgroup (Only Confirmed Pregnancies, Excluding Sites 104 and 120) – Modified Full Analysis Set	T15_02_01_04_06_PI_eval_less_35_B_MI_C_E_mfas
49.	Table 15.2.1.4.7_add Pearl Index Based on Evaluable Cycles in Non-Breastfeeding Women Aged \leq 35 Years by BMI Subgroup (Only Confirmed Pregnancies, Including Sites 104 and 120) – Modified Full Analysis Set	T15_02_01_04_07_PI_eval_less_35_B_MI_C_I_mfas
50.	Table 15.2.1.4.8_add Pearl Index Based on Evaluable Cycles in Non-Breastfeeding Women Aged \leq 35 Years by BMI Subgroup (Confirmed and Suspected, Non-confirmed Pregnancies, Excluding Sites 104 and 120) – Modified Full Analysis Set	T15_02_01_04_08_PI_eval_less_35_B_MI_CS_E_mfas
51.	Table 15.2.1.4.9_add Pearl Index Based on Evaluable Cycles in Non-Breastfeeding Women Aged \leq 35 Years by BMI Subgroup (Confirmed and Suspected, Non-confirmed Pregnancies, Including Sites 104 and 120) – Modified Full Analysis Set	T15_02_01_04_09_PI_eval_less_35_B_MI_CS_I_mfas
52.	Table 15.2.1.4.10_add Pearl Index Based on Evaluable Cycles in Non-Breastfeeding Women Aged \leq 35 Years by Weight Subgroup (Only Confirmed Pregnancies, Excluding Sites 104 and 120) – Modified Full Analysis Set	T15_02_01_04_10_PI_eval_less_35_weight_C_E_mfas
53.	Table 15.2.1.4.11_add Pearl Index Based on Evaluable Cycles in Non-Breastfeeding Women Aged \leq 35 Years by Weight Subgroup (Only Confirmed Pregnancies, Including Sites 104 and 120) – Modified Full Analysis Set	T15_02_01_04_11_PI_eval_less_35_weight_C_I_mfas
54.	Table 15.2.1.4.12_add Pearl Index Based on Evaluable Cycles in Non-Breastfeeding Women Aged \leq 35 Years by Weight Subgroup (Confirmed and Suspected, Non-confirmed Pregnancies, Excluding Sites 104 and 120) – Modified Full Analysis Set	T15_02_01_04_12_PI_eval_less_35_weight_CS_E_mfas
55.	Table 15.2.1.4.13_add Pearl Index Based on Evaluable Cycles in Non-Breastfeeding Women Aged \leq 35 Years by Weight Subgroup (Confirmed and Suspected, Non-confirmed Pregnancies, Including Sites 104 and 120) – Modified Full Analysis Set	T15_02_01_04_13_PI_eval_less_35_weight_CS_I_mfas
56.	Table 15.2.2.1.1 Overall Pregnancy Rate Life Table in Non-Breastfeeding Women (Only Confirmed Pregnancies, Excluding Sites 104 and 120) – Modified Full Analysis Set	T15_02_02_01_01_preg_rate_over_C_E_mfas
57.	Table 15.2.2.1.2 Overall Pregnancy Rate Life Table in Non-Breastfeeding Women Aged \leq 35 Years (Only Confirmed Pregnancies, Excluding Sites 104 and 120) – Modified Full Analysis Set	T15_02_02_01_02_preg_rate_over_les_35_C_E_mfas
58.	Table 15.2.2.1.3 Overall Pregnancy Rate Life Table in Non-Breastfeeding Women Aged $>$ 35 Years (Only Confirmed Pregnancies, Excluding Sites 104 and 120) – Modified Full Analysis Set	T15_02_02_01_03_preg_rate_over_more_35_C_E_mfas

59.	Table 15.2.2.2.1	Evaluable Cycles Pregnancy Rate Life Table in Non-Breastfeeding Women (Only Confirmed Pregnancies, Excluding Sites 104 and 120) – Modified Full Analysis Set	T15_02_02_02_01_preg_rate_eval_C_E_mfas
60.	Table 15.2.2.2.2	Evaluable Cycles Pregnancy Rate Life Table in Non-Breastfeeding Women Aged \leq 35 Years (Only Confirmed Pregnancies, Excluding Sites 104 and 120) – Modified Full Analysis Set	T15_02_02_02_02_preg_rate_eval_les_s_35_C_E_mfas
61.	Table 15.2.2.2.3	Evaluable Cycles Pregnancy Rate Life Table in Non-Breastfeeding Women Aged $>$ 35 Years (Only Confirmed Pregnancies, Excluding Sites 104 and 120) – Modified Full Analysis Set	T15_02_02_02_03_preg_rate_eval_mo_re_35_C_E_mfas
62.	Table 15.2.2.3.1	Method Failure Life Table in Non-Breastfeeding Women (Only Confirmed Pregnancies, Excluding Sites 104 and 120) – Modified Full Analysis Set	T15_02_02_03_01_preg_rate_mf_C_E_mfas
63.	Table 15.2.2.3.2	Method Failure Life Table in Non-Breastfeeding Women Aged \leq 35 Years (Only Confirmed Pregnancies, Excluding Sites 104 and 120) – Modified Full Analysis Set	T15_02_02_03_02_preg_rate_mf_less_35_C_E_mfas
64.	Table 15.2.2.3.3	Method Failure Life Table in Non-Breastfeeding Women Aged $>$ 35 Years (Only Confirmed Pregnancies, Excluding Sites 104 and 120) – Modified Full Analysis Set	T15_02_02_03_03_preg_rate_mf_mor_e_35_C_E_mfas
65.	Table 15.2.3.1.1_add	Overall Pearl Index in Non-Breastfeeding Women (Confirmed and Suspected, Non-confirmed Pregnancies, Including Sites 104 and 120) – Modified Full Analysis Set	T15_02_03_01_01_PI_over_CS_I_mfas
66.	Table 15.2.3.1.2_add	Overall Pearl Index in Non-Breastfeeding Women (Only Confirmed Pregnancies, Including Sites 104 and 120) – Modified Full Analysis Set	T15_02_03_01_02_PI_over_C_I_mfas
67.	Table 15.2.3.1.3_add	Overall Pearl Index in Non-Breastfeeding Women (Confirmed and Suspected, Non-confirmed Pregnancies, Excluding Sites 104 and 120) – Modified Full Analysis Set	T15_02_03_01_03_PI_over_CS_E_mfas
Safety Data			
68.	Table 15.3.1.1.1	Summary of Adverse Events – Safety Set	T15_03_01_01_01_ae_ss
69.	Table 15.3.1.1.2	Summary of Adverse Events by Weight Subgroup – Safety Set	T15_03_01_01_02_ae_weight_ss
70.	Table 15.3.1.1.3	Summary of Adverse Events by BMI Subgroup – Safety Set	T15_03_01_01_03_ae_bmi_ss
71.	Table 15.3.1.1.4	Summary of Adverse Events by Blood Pressure Subgroup – Safety Set	T15_03_01_01_04_ae_blood_ss
72.	Table 15.3.1.1.5	Summary of Adverse Events by Race Subgroup – Safety Set	T15_03_01_01_05_ae_race_ss
73.	Table 15.3.1.1.6	Summary of Adverse Events by Ethnicity Subgroup – Safety Set	T15_03_01_01_06_ae_ethnicity_ss
74.	Table 15.3.1.2.1	Incidence of TEAEs – Safety Set	T15_03_01_02_01_tae_ss
75.	Table 15.3.1.2.2	Incidence of TEAEs by Weight Subgroup – Safety Set	T15_03_01_02_02_tae_weight_ss
76.	Table 15.3.1.2.3	Incidence of TEAEs by BMI Subgroup – Safety Set	T15_03_01_02_03_tae_bmi_ss
77.	Table 15.3.1.2.4	Incidence of TEAEs by Blood Pressure Subgroup – Safety Set	T15_03_01_02_04_tae_blood_ss
78.	Table 15.3.1.2.5	Incidence of TEAEs by Race Subgroup – Safety Set	T15_03_01_02_05_tae_race_ss
79.	Table 15.3.1.2.6	Incidence of TEAEs by Ethnicity Subgroup – Safety Set	T15_03_01_02_06_tae_ethnicity_ss
80.	Table 15.3.1.3.1	Incidence of TEAEs by Relationship – Safety Set	T15_03_01_03_01_tae_rel_ss
81.	Table 15.3.1.3.2	Incidence of TEAEs by Relationship by Weight Subgroup – Safety Set	T15_03_01_03_02_tae_rel_weight_ss
82.	Table 15.3.1.3.3	Incidence of TEAEs by Relationship by BMI Subgroup – Safety Set	T15_03_01_03_03_tae_rel_bmi_ss

83.	Table 15.3.1.3.4	Incidence of TEAEs by Relationship by Blood Pressure Subgroup – Safety Set	T15_03_01_03_04_teae_rel_blood_ss
84.	Table 15.3.1.3.5	Incidence of TEAEs by Relationship by Race Subgroup – Safety Set	T15_03_01_03_05_teae_rel_race_ss
85.	Table 15.3.1.3.6	Incidence of TEAEs by Relationship by Ethnicity Subgroup – Safety Set	T15_03_01_03_06_teae_rel_ethnicity_ss
86.	Table 15.3.1.4.1	Incidence of TEAEs by Worst Severity – Safety Set	T15_03_01_04_01_teae_sev_ss
87.	Table 15.3.1.4.2	Incidence of TEAEs by Worst Severity by Weight Subgroup – Safety Set	T15_03_01_04_02_teae_sev_weight_ss
88.	Table 15.3.1.4.3	Incidence of TEAEs by Worst Severity by BMI Subgroup – Safety Set	T15_03_01_04_03_teae_sev_bmi_ss
89.	Table 15.3.1.4.4	Incidence of TEAEs by Worst Severity by Blood Pressure Subgroup – Safety Set	T15_03_01_04_04_teae_sev_blood_ss
90.	Table 15.3.1.4.5	Incidence of TEAEs by Worst Severity by Race Subgroup – Safety Set	T15_03_01_04_05_teae_sev_race_ss
91.	Table 15.3.1.4.6	Incidence of TEAEs by Worst Severity by Ethnicity Subgroup – Safety Set	T15_03_01_04_06_teae_sev_ethnicity_ss
92.	Table 15.3.1.5.1	Incidence of Serious TEAEs – Safety Set	T15_03_01_05_01_saeteae_ss
93.	Table 15.3.1.5.2	Incidence of Serious TEAEs by Weight Subgroup – Safety Set	T15_03_01_05_02_saeteae_weight_ss
94.	Table 15.3.1.5.3	Incidence of Serious TEAEs by BMI Subgroup – Safety Set	T15_03_01_05_03_saeteae_bmi_ss
95.	Table 15.3.1.5.4	Incidence of Serious TEAEs by Blood Pressure Subgroup – Safety Set	T15_03_01_05_04_saeteae_blood_ss
96.	Table 15.3.1.5.5	Incidence of Serious TEAEs by Race Subgroup – Safety Set	T15_03_01_05_05_saeteae_race_ss
97.	Table 15.3.1.5.6	Incidence of Serious TEAEs by Ethnicity Subgroup – Safety Set	T15_03_01_05_06_saeteae_ethnicity_ss
98.	Table 15.3.1.6.1	Incidence of TEAEs Leading to Trial Termination – Safety Set	T15_03_01_06_01_teae_term_ss
99.	Table 15.3.1.6.2	Incidence of TEAEs Leading to Trial Termination by Weight Subgroup – Safety Set	T15_03_01_06_02_teae_term_weight_ss
100.	Table 15.3.1.6.3	Incidence of TEAEs Leading to Trial Termination by BMI Subgroup – Safety Set	T15_03_01_06_03_teae_term_bmi_ss
101.	Table 15.3.1.6.4	Incidence of TEAEs Leading to Trial Termination by Blood Pressure Subgroup – Safety Set	T15_03_01_06_04_teae_term_blood_ss
102.	Table 15.3.1.6.5	Incidence of TEAEs Leading to Trial Termination by Race Subgroup – Safety Set	T15_03_01_06_05_teae_term_race_ss
103.	Table 15.3.1.6.6	Incidence of TEAEs Leading to Trial Termination by Ethnicity Subgroup – Safety Set	T15_03_01_06_06_teae_term_ethnicity_ss
104.	Table 15.3.1.7.1	Incidence of TEAEs of Special Interest – Safety Set	T15_03_01_07_01_teae_sp_int_ss
105.	Table 15.3.1.7.2	Incidence of TEAEs of Special Interest by Weight Subgroup – Safety Set	T15_03_01_07_02_teae_sp_int_weight_ss
106.	Table 15.3.1.7.3	Incidence of TEAEs of Special Interest by BMI Subgroup – Safety Set	T15_03_01_07_03_teae_sp_int_bmi_ss
107.	Table 15.3.1.7.4	Incidence of TEAEs of Special Interest by Blood Pressure Subgroup – Safety Set	T15_03_01_07_04_teae_sp_int_blood_ss
108.	Table 15.3.1.7.5	Incidence of TEAEs of Special Interest by Race Subgroup – Safety Set	T15_03_01_07_05_teae_sp_int_race_ss
109.	Table 15.3.1.7.6	Incidence of TEAEs of Special Interest by Ethnicity Subgroup – Safety Set	T15_03_01_07_06_teae_sp_int_ethnicity_ss
110.	Table 15.3.1.8.1	Incidence of Related Serious TEAEs – Safety Set	T15_03_01_08_01_rel_saeteae_ss
111.	Table 15.3.1.8.2	Incidence of Related Serious TEAEs by Weight Subgroup – Safety Set	T15_03_01_08_02_rel_saeteae_weight_ss
112.	Table 15.3.1.8.3	Incidence of Related Serious TEAEs by BMI Subgroup – Safety Set	T15_03_01_08_03_rel_saeteae_bmi_ss
113.	Table 15.3.1.8.4	Incidence of Related Serious TEAEs by Blood Pressure Subgroup – Safety Set	T15_03_01_08_04_rel_saeteae_blood_ss

114.	Table 15.3.1.8.5	Incidence of Related Serious TEAEs by Race Subgroup – Safety Set	T15_03_01_08_05_rel_saeteae_race_ss
115.	Table 15.3.1.8.6	Incidence of Related Serious TEAEs by Ethnicity Subgroup – Safety Set	T15_03_01_08_06_rel_saeteae_ethnicity_ss
116.	Table 15.3.2.1.1	Summary of Vital Signs – Safety Set	T15_03_02_01_01_vs_ss
117.	Table 15.3.2.1.2	Summary of Vital Signs by Weight Subgroup – Safety Set	T15_03_02_01_02_vs_weight_ss
118.	Table 15.3.2.1.3	Summary of Vital Signs by BMI Subgroup – Safety Set	T15_03_02_01_03_vs_bmi_ss
119.	Table 15.3.2.1.4	Summary of Vital Signs by Blood Pressure Subgroup – Safety Set	T15_03_02_01_04_vs_blood_ss
120.	Table 15.3.2.1.5	Summary of Vital Signs by Race Subgroup – Safety Set	T15_03_02_01_05_vs_race_ss
121.	Table 15.3.2.1.6	Summary of Vital Signs by Ethnicity Subgroup – Safety Set	T15_03_02_01_06_vs_ethnicity_ss
122.	Table 15.3.3.1.1	Summary of Clinical Laboratory Tests: Hematology – Safety Set	T15_03_03_01_01_hema_ss
123.	Table 15.3.3.1.2	Summary of Clinical Laboratory Tests: Biochemistry – Safety Set	T15_03_03_01_02_bioch_ss
124.	Table 15.3.3.1.3	Summary of Clinical Laboratory Tests: Urinalysis dipstick – Safety Set	T15_03_03_01_03_urin_ss
125.	Table 15.3.3.1.4	Clinical Laboratory Tests: Incidence of Hematology Abnormalities – Safety Set	T15_03_03_01_04_hema_abn_ss
126.	Table 15.3.3.1.5	Clinical Laboratory Tests: Incidence of Biochemistry Abnormalities – Safety Set	T15_03_03_01_05_bioch_abn_ss
127.	Table 15.3.3.1.6	Clinical Laboratory Tests: Shift Table of Hematology Results – Safety Set	T15_03_03_01_06_shift_hema_ss
128.	Table 15.3.3.1.7	Clinical Laboratory Tests: Shift Table of Biochemistry Results – Safety Set	T15_03_03_01_07_shift_bioch_ss
